#### **Safety Assessments**

AEs; clinical laboratory values (serum chemistry and hematology studies); standard 12-lead ECGs; echocardiograms; vital signs; and physical examinations.

# **Exploratory Assessments**

#### **Statistical Analyses**

#### **Bayesian Adaptive Model:**

The adaptive BLRM with EWOC principle will be used, with the following 2 exceptions:

- 1. For cohorts requiring 3 or more evaluable subjects, if only 2 evaluable subjects are available for assessment (all others drop out), and neither subject has had a treatment-related or possibly-related toxicity greater than CTCAE Grade 1, then 2 subjects will be considered sufficient for decision-making
- 2. If the first 2 subjects in a cohort have DLTs, no additional subjects will be enrolled into that cohort until the Bayesian model has been updated with this new information. Likewise, the model will be re-evaluated if 2 subjects in a cohort have DLTs before the enrollment of any additional subjects.

Model:

$$logit\{\pi(d_j, x_1, ..., x_k)\} = \log(\alpha) + \beta \log\left(\frac{d_j}{d^*}\right) + \sum_{i=1}^k \gamma_i x_i$$

 Under-dosing:
  $\pi(d) \in [0.00, 0.166)$  

 Target toxicity:
  $\pi(d) \in [0.166, 0.333)$  

 Excessive toxicity:
  $\pi(d) \in [0.333, 1.00]$ 

The recommended dose for the next cohort will fulfill the following 2 criteria:

- 1. Dose that maximizes probability that true DLT rate is in the target toxicity interval [0.166, 0.333)
- 2. With overdose control: less than 25% probability of the true DLT rate in the excessive toxicity interval [0.333, 1].

#### **Data Analyses:**

Analysis of all data will be performed by the sponsor or designee. The demographics and baseline characteristics will be summarized by dose group, by concurrent regimen and study part, and overall. Baseline characteristics will include but will not be limited to the following variables: type of cancer, tumor stage at baseline, World Health Organization (WHO) performance status at baseline, time elapsed since cancer diagnosis, prior chemotherapy and radiation therapy, and duration of most recent cancer therapy.

The overall safety profile of VX-984 will be assessed in terms of the following primary safety endpoints:

- Incidence of treatment-emergent AEs (TEAEs), including AEs leading to dose modifications or discontinuations
- Incidence of DLTs (Part A)
- Clinical laboratory values
- ECG outcomes
- Echocardiogram outcomes
- Vital signs.

Safety data will be summarized by dose group, by concurrent regimen and study part, and overall. In general, safety analyses will be based on the Safety Set defined as all subjects who have received any study drug.

The summary of DLTs will be based on the DLT Evaluable Set. The BLRM will be used to estimate the posterior distributions for the probabilities of DLT events at various combination dose levels after each cohort of subjects. The MTD is defined as the combination dose associated with the highest probability that DLT events will occur in 16.6% to less than 33.3% subjects and as the combination dose that will not exceed the overdose criterion (<25% probability that DLT events will occur in  $\ge 33\%$  of subjects).

Efficacy data will be summarized by dose group, by concurrent regimen and study part, and overall. For Part B, the proportion of subjects demonstrating ORR, together with exact 90% CI, will be presented.

VX-984 PK data will be analyzed on an ongoing basis during dose escalation in Parts A and B using standard noncompartmental methods. PK data for VX-984 will be reviewed with safety data to inform dose escalation.

## 3 SCHEDULE OF ASSESSMENTS

Schedules of Assessments are shown in Table 3-1, Table 3-2, and Table 3-3.

Table 3-1 Study VX15-984-001: Screening (Parts A and B)

Assessment	Screening Visit Day -28 to Day -15 (Part A with Lead-in Period) Day -14 to Day -1 (Part A without Lead-in Period and Part B)
Informed consent	X
Demographics	X
Medical history	X
Prior and concomitant medications	X
Height, weight, BMI, and vital signs	X
Physical examination a	X
Radiological (CT) disease assessment b	X
Bone scan c	X
Transthoracic echocardiogram d	X
Clinical disease assessment e	X
WHO performance status	X
Standard 12-lead electrocardiogram (ECG)	X
Serum FSH (postmenopausal female subjects only)	X
Serum β-HCG (all female subjects)	X
Serum chemistry	X
Hematology	X
Coagulation	X
Urinalysis	X
Thyroid-stimulating hormone	X
CCI	

- a Physical examination of all body systems.
- Subjects will have a chest and abdominal CT scan and, if clinically indicated, a pelvic CT scan. Radiologic scans performed within 2 weeks of Screening may substitute for assessment of eligibility; however, for Part B, CT scan must be repeated during Screening according to the Imaging Manual unless discussed with the sponsor.
- For all subjects with prostate cancer or for subjects with other malignancies in whom bony metastases have been previously documented or are highly suspected. Results of a bone scan performed within 4 weeks before Screening may substitute for the Screening bone scan. If results from a PET CT scan are available, they may be used to substitute for a bone scan.
- If an echocardiogram or nuclear scan has been performed within 1 month before Screening, these results may be used, unless repetition of the assessment is clinically indicated.
- e Assessment includes tumor staging (I to IV) and Tumor-Node-Metastasis.

f	CCI		
	CCI		
		·	

Table 3-1 Study VX15-984-001: Screening (Parts A and B)

Assessment	Screening Visit Day -28 to Day -15 (Part A with Lead-in Period) Day -14 to Day -1 (Part A without Lead-in Period and Part B)
Historical CT scans (optional) g	X
Adverse events	Continuous from signing of Informed Consent Form (ICF) through Safety Follow-up Visit

g If accessible, the last 2 CT scans taken before the Screening scan will be collected from enrolled subjects.

Outpatient Visit         X         X         X           Safety Assessments           Physical examination b X                     WHO performance status         X                     WHO performance status         X                     Vital signs         X°                     12-lead ECG         X d             Serum chemistry e X         X           Hematology e X         X           Urine β-hCG f X                     Urinalysis         X                     Concomitant medications and AEs         Continuous from signing of ICF through Safety Follow-up Visit           Study Drug Administration                               VX-984 dosing g X         X         X           Pharmacokinetic Assessments   VX-984 (Plasma PK collection)         X h X h X h VX-984 (Urine PK collection)         X i X i X i		Lead-in (Part A) a Day -14 Day -13 Day -12 Day -11 Day -10 Day -9										
Safety Assessments         Physical examination b       X       Image: street of the collection b       X       Image: street of the collection b       Image: street of the collection b       X       Image: street of the collection b       <	Assessment	Day -14	Day -13	Day -12	Day -11	Day -10	Day -9					
Physical examination b       X       Sexecute the second of the	Outpatient Visit	X		X	X							
$\begin{array}{c ccccccccccccccccccccccccccccccccccc$	Safety Assessments											
$\begin{array}{c ccccccccccccccccccccccccccccccccccc$	Physical examination b	X										
12-lead ECG $X^d$ $X$ $X$ Serum chemistrye $X$ $X$ $X$ Hematologye $X$ $X$ $X$ Urine β-hCGf $X$ $X$ $X$ Urinalysis $X$ $X$ $X$ Concomitant medications and AEs       Continuous from signing of ICF through Safety Follow-up Visit         Study Drug Administration $X$ $X$ VX-984 dosings $X$ $X$ $X$ Pharmacokinetic Assessments $X$ $X$ $X$ VX-984 (Plasma PK collection) $X$		X										
Serum chemistrye       X       X         Hematologye       X       X         Urine β-hCGf       X       Image: Concommon signification of ICF through Safety Follow-up Visit AEs         Study Drug Administration       Image: Concommon signification of ICF through Safety Follow-up Visit AEs         Study Drug Administration       Image: Concommon signification of ICF through Safety Follow-up Visit AEs         VX-984 dosingg       X       X       X         VX-984 (Plasma PK collection)       Xh       Xh       Xh         VX-984 (Urine PK collection)       Xi       Xi       Xi	Vital signs	Xc										
Hematologye       X       X         Urine β-hCGf       X       Image: Concomplete of the continuous of the continuo	12-lead ECG	X d										
Urine β-hCGf       X       Image: Continuous from the c	Serum chemistry e	X		X								
Urinalysis     X     Concomitant medications and AEs       Study Drug Administration     Continuous from signing of ICF through Safety Follow-up Visit AX Start AX	Hematology e	X		X								
Concomitant medications and AEs  Study Drug Administration  VX-984 dosing g VX-984 (Plasma PK collection)  VX-984 (Urine PK collection)  Continuous from signing of ICF through Safety Follow-up Visit  X X X X  X X X  YX  VX-984 (Plasma PK collection)  X Y X X X  VX-984 (Urine PK collection)	Urine β-hCG f	X										
AEs         Study Drug Administration         VX-984 dosingg         X	Urinalysis	X										
VX-984 dosing g X         X         X           Pharmacokinetic Assessments         Xh         Xh           VX-984 (Plasma PK collection)         Xh         Xh           VX-984 (Urine PK collection)         Xi         Xi		Continuo	ous from sign	ning of ICF	through Saf	ety Follow-u	ıp Visit					
Pharmacokinetic Assessments         Xh         Xh           VX-984 (Plasma PK collection)         Xi         Xi           VX-984 (Urine PK collection)         Xi         Xi	Study Drug Administration											
VX-984 (Plasma PK collection)  VX-984 (Urine PK collection)  Xh  Xi  Xi  Xi	VX-984 dosing g	X	X	X								
VX-984 (Urine PK collection) X i X i	Pharmacokinetic Assessments											
	VX-984 (Plasma PK collection)			X h	X h							
Exploratory Assessments	VX-984 (Urine PK collection)			Xi	Xi							
	Exploratory Assessments											

- a There will be a Lead-in Period of VX-984 monotherapy for all cohorts in Part A in which the administered dose will be higher than any previously evaluated dose of VX-984 as monotherapy in at least 3 subjects.
- b Symptom-directed physical examinations will be performed as clinically indicated in the Investigator's judgment.
- $^{\circ}$  Vital signs will be measured before dosing and 4 (± 1) hours after dosing.
- d 12-lead ECG will be measured up to 60 minutes before dosing and 2 and 4 hours after dosing (± 60 minutes).
- e Laboratory results should be reviewed before dosing on days of study drug administration. To facilitate timely administration of study drug, safety labs may be performed the day before dosing. If labs are drawn the evening before, they should be recorded as corresponding to day of planned drug administration. Laboratory values must conform to inclusion/exclusion criteria for study drug administration.
- f Female subjects of childbearing potential only. Assessment should be performed before dosing.
- g Subjects will receive study drug in the clinic on Days -14 and -12; and at home on Day -13. Subjects will take study drug at home per instructions provided in Section 10.3.
- h Plasma PK samples will be collected on Day -12 before dosing (0 hour) and at 0.5, 1, 2, 4, 8, and 24 hours (Day -11) after dosing.
- i Urine PK samples will be collected before dosing (0 hour) and from 0 to 4, 4 to 8, and 8 to 24 hours (Day -11) after dosing.
- i CCI
- k (;(;

Event/Assessment	Day 1	Day 2	Day 3	Day 4	Day 5	Day 8	Day 15	Follo	w-up a
During Each Cycle (Except as Noted)		·			·		·	28 days (± 7 days)	5 weeks (± 1 week)
Outpatient visits	X	$X^{b,c}$		Xb	Xb	X	X	X	X
Safety Assessments									
Physical examination d	X							X	
CT scan disease assessment e	At the end	of every 2		st 6 cycles the		f every 2 to 3	cycles until		X
Clinical disease assessment g	X								X
Bone scan h		At the	end of every	4 to 6 cycles	until disease p	progressionf	•		
Transthoracic echocardiogram		At the end of every 2 cycles until disease progression f							
WHO performance status	X							X	
Weight	X							X	
Vital signs	Xi	$X^{b,i}$						X	
12-lead ECG	X j	$X^{b,j}$						X	
Serum chemistry	$X^k$				Xb	X	X	X	
Hematology	$X^k$					X	X	X	
Urine β-hCG 	X							X	
Concomitant medications		Continuous from signing of ICF through Safety Follow-up Visit						X	
AEs		Continuous from signing of ICF through Safety Follow-up Visit						X	
Study Drug Administration									
VX-984 m		X	X	X					
PLD	X								
Pharmacokinetic Assessments									

<sup>a Follow-up will include a Safety Follow-up Visit 28 (± 7) days after the last dose of study drug and a radiologic Follow-up Visit 5 (±1) weeks after the last cycle of chemotherapy, and survival follow-up assessment at the last subject last visit. In Part B, for subjects without disease progression, long-term follow-up, including as indicated staging CT scans and/or follow-up communications, may continue for up to 1 year. See Section 8.1.4 for additional details.

b Cycle 1 only.

<sup>c Day 2 visit is required for Part A only.

d Symptom-directed physical examinations will be performed as clinically indicated in the Investigator's judgment.

Table 3-3 Study VX15-	able 3-3 Study VX15-984-001: VX-984 and PLD Combination Therapy and Follow-up (Parts A and B)									
Event/Assessment	Day 1	Day 2	Day 3	Day 4	Day 5	Day 8	Day 15	Follo	w-up a	
During Each Cycle								28 days	5 weeks	
(Except as Noted)								(± 7 days)	(± 1 week)	
Part A VX-984 (Plasma PK collection)		X n		X n	X n					
Part A PLD (Plasma PK collection)	Xº	Xº		Xº	Xº					
Part B VX-984 (Plasma PK collection)				$X^p$						

<sup>e CT scan of chest, abdomen, and pelvis should be performed, in addition to CT scan of other body areas, as clinically indicated.

<sup>f End of cycle assessments may be performed up to 5 days before Day 1 of subsequent cycle.

<sup>g Assessment includes tumor staging (I to IV) and Tumor-Node-Metastasis.

h For all subjects with prostate cancer or for subjects with other malignancies in whom bony metastases have been previously documented or are highly suspected; or if clinically indicated.

Vital signs will be measured on Day 1 up to 60 minutes before administration of PLD and on Day 2 up to 60 minutes before administration of VX-984 and at 2 (± 1) hours after administration of VX-984.

<sup>j 12-lead ECG will be measured on Day 1 up to 60 minutes before administration of PLD. ECG will be measured on Day 2 only during Cycle 1 and will be measured up to 60 minutes before administration of VX-984, and 2 and 4 hours (± 60 minutes) after administration of VX-984.

<sup>k To facilitate timely administration of study drug on Day 1, safety lab samples may be collected up to 3 days before Day 1. If safety lab samples are collected before Day 1, they should be recorded as corresponding to Day 1.

<sup>1 Female subjects of childbearing potential only.

<sup>m For Part A: For Cycle 1, subjects will receive VX-984 in the clinic on Days 2 and 4; and at home on Day 3. After Cycle 1, subjects will be instructed to take all VX-984 doses at home per instructions provided in Section 10.3.

For Part B: For Cycle 1, subjects will receive VX-984 in the clinic on Day 4 or the day subjects come in for PK assessment; and at home on Days 2 and 3. After Cycle 1, subjects will be instructed to take all VX-984 doses at home per instructions provided in Section 10.3.

<sup>n Cycle 1 only. VX-984 plasma PK samples will be collected on Day 2 before dosing (0 hour) and at 0.5, 1, 2, and 4 hours after dosing; and on Day 4 before dosing (0 hour) and at 0.5, 1, 2, 4, 8, and 24 hours (Day 5) after dosing.

Ocycle 1 only. PLD plasma PK samples will be collected on Day 1 before beginning of infusion (BOI) and at 1, 2, 4, 6, 24 hours (Day 2), 72 hours (Day 4) and 96 hours (Day 5) after BOI.

<sup>p Cycle 1 only. VX-984 plasma PK samples will be collected on Day 4 before dosing (0 hour) and at 0.5, 1, 2, 4, and 8 hours after dosing. PK sampling may occur on Days 2 or 3 if subjects are unable to come to the clinic on Day 4. PK samples are required from a minimum of 20 subjects.

Table 3-3 Study VX15-984-001: VX-984 and PLD Combination Therapy and Follow-up (Parts A and B)									
Event/Assessment	Day 1	Day 2	Day 3	Day 4	Day 5	Day 8	Day 15	Follow	w-up a
During Each Cycle (Except as Noted)								28 days (± 7 days)	5 weeks (± 1 week)
Part B PLD (Plasma PK collection)				X q					
Exploratory Assessments									

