## 8 STUDY DESIGN

## 8.1 Overview of Study Design

This is an open-label, multicenter, single-arm, FIH, dose-escalation study in subjects with solid tumors who have progressed through standard therapeutic options and for whom no standard therapy is available or PLD may be considered SOC (Part A) followed by an expansion phase in subjects with recurrent or metastatic endometrial cancer who have progressed on a prior platinum regimen (Part B).

Part A will be a dose escalation study to evaluate the safety, tolerability, and PK of VX-984 when administered in combination with PLD. At each VX-984 dose level tested, subjects will receive VX-984 once daily (qd) alone on Days -14 to -12 of a 14-day Lead-in Period before receiving combination treatment with PLD. Following the single agent Lead-in Period, subjects will receive PLD on Day 1 and VX-984 qd on Days 2 to 4 of a 28-day cycle. The Lead-in Period will be required only if the dose of VX-984 is escalated beyond the highest dose of VX-984 previously tolerated in a Lead-in Period. This part will establish the MTD of VX-984 in combination with PLD (Figure 8-1).

Part B will be an expanded cohort study to confirm the safety, tolerability, PK, and potential anti-tumor activity of VX-984 in combination with PLD at the MTD or lower, as determined during Part A (Figure 8-1).

[figure not shown]

Figure 8-1 Overview of Study Design

- a. The Lead-in Period will be required only if the dose of VX-984 exceeds a dose previously tolerated in a Lead-in Period.
- b. Subjects in Part A will receive up to 6 cycles of treatment. Subjects with tumors responding to treatment may continue on treatment past 6 cycles with the agreement of the Investigator and medical monitor.
- Subjects in Part B will receive treatment until disease progression, unacceptable toxicity, or withdrawal of consent.
- d. Follow-up will include a Safety Follow-up Visit 28 (± 7) days after the last dose of study drug and a radiologic follow-up visit 5 (± 1) weeks after the last cycle of chemotherapy, and survival follow-up assessment at the last subject last visit. In Part B, for subjects without disease progression, long-term follow-up, including, as indicated, staging CT scans and/or follow-up communications, may continue for up to 1 year.

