## 8.1.2.1.1 Starting Dose and Dosing Schedule

The starting dose of VX-984 will be 120 mg qd and PLD will be 40 mg/m^2. The rationale for selection of the starting dose and dosing schedule for VX-984 and PLD is provided in Section 8.2.2.

For each VX-984 dose level tested, subjects will receive VX-984 qd alone on Days -14 to -12 of a 14-day Lead-in Period. Following the single agent Lead-in Period, subjects will receive PLD on Day 1 and VX-984 qd on Days 2 to 4 of a 28-day cycle. The Lead-in Period will be required only if the dose of VX-984 is escalated beyond the highest dose of VX-984 previously tolerated in a Lead-in Period.

Criteria for study drug administration on Day 1 of Cycle 1 and subsequent cycles are summarized in Section 10.2.

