- In the event of a DLT, an adaptive Bayesian logistic regression model (BLRM) will be used to determine the dose for the subsequent cohorts or determine if the current dose level should be expanded. The adaptive BLRM will be guided by the escalation overdose control (EWOC) principle to control the risk of DLT in future subjects as described in Section 12.3.3.2. At each predicted dose, 3 to 6 subjects will be enrolled in each cohort at the discretion of the sponsor and Investigators as described in Section 8.1.2.1.8. If more than 3 subjects are enrolled, the first 3 subjects will receive VX-984 in the Lead-in Period and if no DLT is observed with VX-984 dosing then the additional subjects in the cohort will not have the Lead-in Period. The Lead-in Period will be required only if the dose of VX-984 is escalated beyond the highest dose of VX-984 previously tolerated in a Lead-in Period
- If 2 subjects in a previously untested dose level experience a DLT, enrollment to that cohort will stop, the BLRM will be updated and the next cohort will be opened at a lower dose level or an intermediate dose level that satisfies the EWOC criteria. However, if 2 subjects in a new cohort at a previously tested dose level experience a DLT (e.g., a total of 8 subjects are tested on this dose level with 2 DLTs observed), further enrollment to that cohort will stop, the BLRM will be updated with this new information and re-evaluation of the available safety, PK and PD data will occur. By

incorporating information gained at the preceding dose levels, additional subjects may be enrolled into the current dose level only if the dose still meets the EWOC criteria and as agreed by the sponsor and Investigators.

A subject will be considered as evaluable for dose determination if they have a DLT during Cycle 1 or the preceding Lead-in Period, or meet the minimum treatment and safety evaluation requirements for the first cycle as outlined in Subject Evaluability.

After completion of Cycle 1 of each cohort (3 to 6 subjects), available safety, PK, and efficacy information as well as recommendations from the Bayesian model will be used to determine the dose for the next cohort, with the following 2 exceptions:

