- 1. For cohorts requiring 3 or more evaluable subjects, if only 2 evaluable subjects are available for assessment (all others drop out), and neither subject has had a treatment-related or possibly-related toxicity greater than CTCAE Grade 1, then 2 subjects will be considered sufficient for decision-making
- 2. If the first 2 subjects in a cohort have a DLT, further enrollment to the study will be temporarily suspended and the Bayesian model will be updated with this new information. If the Bayesian model supports enrolling the next cohort at the dose level where 2 DLTs occurred, or at a higher dose level, the relevant data and rationale will be discussed and agreed upon by sponsor and the Investigators of the escalation phase. If sponsor and the Investigators agree that it is medically appropriate to enroll an additional cohort at the dose level where 2 DLTs occurred or at a higher dose, the data and rationale supporting this decision will be documented.

Following the principle of escalation with overdose control (EWOC), after each cohort the recommended dose will be the one with the highest posterior probability of the DLT rate falling in the target toxicity interval [0.166, 0.333) among the doses fulfilling EWOC. Per EWOC, it should be unlikely (< 25% posterior probability) that the DLT rate at the dose will exceed 0.333.

For further understanding of the safety, tolerability, and PK of VX 984 in combination with PLD, additional cohorts of subjects may be enrolled at preceding dose levels, or to intermediate dose levels before or while proceeding with further dose escalation. The maximum planned dose of VX-984 is 2000 mg during escalation, however, higher doses up to 3000 mg may be allowed depending on the observed safety, PK, and PD, and based on recommendation of the BLRM.

After repeating the above steps, the dose escalation of VX-984 will continue with a constant dose of PLD at 40 mg/m^2 until MTD is achieved.

If a dose of VX-984 is not tolerated with PLD at 40 mg/m², then the VX-984 dose may be reduced by up to 50% with a constant dose of PLD at 40 mg/m² or the dose of PLD will be reduced by 25% (30 mg/m²) or lower with a constant dose of VX-984. These doses will be explored in subsequent cohorts at the discretion of the Investigators and sponsor. If daily dosing of VX-984 for 3 days after PLD is not tolerated during initial dose escalation, less frequent dosing of VX-984 may be explored in subsequent cohorts.

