## 8.1.2.1.5 Determination of MTD

Definition of MTD: The MTD is defined as the highest dose combination for a given schedule that causes DLTs in no more than 33.3% of subjects during the first cycle of treatment.

Dose escalation will continue until the identification of MTD or a suitable lower dose for Part B. This will occur when the following conditions are met:

- 1. at least 6 subjects have been treated at this dose
- 2. the dose satisfies one of the following conditions:
  - a. the posterior probability of targeted toxicity at this dose exceeds 50% and is the highest among potential doses, or
  - b. at least 15 subjects have been treated

The DLT Evaluable Set will be used for the determination of the MTD.

b. Dose level -1 represents a dose that may be evaluated if dose level 1 (starting doses of VX-984 and PLD) is poorly tolerated.

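### The schedule table triggers the Lead-in Period by the highest VX-984 dose evaluated alone, the body text by the highest dose tolerated, and the two rules can give different instructions for the same cohort

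*Protocol*

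**What the plan says.** The Protocol states the Lead-in trigger in several places.

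- **Section 3, Table 3-2 footnote a:** there will be a Lead-in for Part A cohorts "in which the administered dose will be higher than any previously evaluated dose of VX-984 as monotherapy in at least 3 subjects".
- **Section 8.1.2.1.1:** the Lead-in is required "only if the dose of VX-984 is escalated beyond the highest dose of VX-984 previously tolerated in a Lead-in Period". The synopsis (starting dose and escalation guidelines), the text of Section 8.1 and Section 8.1.2.1.2 give the same rule.
- **Figure 8-1 note a:** the Lead-in is required only if the VX-984 dose "exceeds a dose previously tolerated in a Lead-in Period". This keeps *tolerated* but omits *highest*.
- **Section 8.1.2.1.2, larger cohorts:** "the first 3 subjects will receive VX-984 in the Lead-in Period and if no DLT is observed with VX-984 dosing", then the added subjects in that cohort skip it. This waiver depends on both a count of 3 and the outcome.

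Section 8.1.2.1.2 foresees toxicity during the Lead-in, since a subject is evaluable for dose determination "if they have a DLT during Cycle 1 or the preceding Lead-in Period". It also provides for cohorts below a failed dose. After 2 DLTs at an untested level, "the next cohort will be opened at a lower dose level or an intermediate dose level that satisfies the EWOC criteria". More generally, "additional cohorts of subjects may be enrolled at preceding dose levels, or to intermediate dose levels".

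Neither document defines what makes a dose tolerated in a Lead-in, or says which trigger governs if they disagree. The SAP drops Part B but keeps Part A, where the Lead-in belongs, and does not restate the trigger.

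**The concern.** *Evaluated* ignores the outcome and *tolerated* depends on it. Once a dose has been given alone to 3 subjects it counts as evaluated, even if it proved too toxic. From then on, the footnote asks for no Lead-in at or below that dose.

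Staff working from the schedule could therefore omit the single-agent period just after single-agent toxicity, in a first-in-human study. Subjects would start directly on PLD plus a VX-984 dose above the highest one tolerated alone.

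What they would miss is limited but real:

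- The Lead-in has chemistry and hematology on Days -14 and -12, and laboratory results are to be reviewed before dosing.
- In Cycle 1, after the Day 1 draw, chemistry resumes on Day 5 and hematology on Day 8. Both come after the last VX-984 dose on Day 4.
- Urine PK is scheduled only in the Lead-in.
- Toxicity that appears after PLD is harder to attribute to VX-984, and the safety of VX-984 alone is part of a Part A primary objective.

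**Working it through.** The plan gives no figure to reproduce, so the check compares the two rules.

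**Definitions**

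- *d*: VX-984 dose of the next cohort.
- *T*: highest dose tolerated in a Lead-in. The body text calls for a Lead-in if *d* > *T*.
- *E*: highest dose given alone to at least 3 subjects. The footnote calls for a Lead-in if *d* > *E*.
- *S*: highest dose tolerated alone, without DLT, in at least 3 subjects. This is the proposed common rule: Lead-in if *d* > *S*.

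The rules disagree in two ranges:

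- *T* < *d* ≤ *E*: the body text calls for a Lead-in, the footnote does not.
- *E* < *d* ≤ *T*: the footnote calls for a Lead-in, the body text does not.

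**Cases**, using Table 8-1 doses (120, 240, 480 and 720 mg) and assumed outcomes. The 360 mg dose is an illustrative intermediate dose, 480 × 0.75 = 360.

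| Case | T | E | S | d | Body text | Footnote | Proposed |
|---|---|---|---|---|---|---|---|
| A. 240 tolerated in 3; 480 given alone to 3, not tolerated | 240 | 480 | 240 | 360 | yes (360 > 240) | no (360 < 480) | yes |
| B. As A, new cohort back at 480 | 240 | 480 | 240 | 480 | yes (480 > 240) | no (480 = 480) | yes |
| C. As A, but only 2 subjects took 480 alone | 240 | 240 | 240 | 360 | yes | yes | yes |
| D. 480 tolerated alone in 3 | 480 | 480 | 480 | 360 | no | no | no |
| E. 120 tolerated in 3; 240 tolerated alone in only 2 | 240 | 120 | 120 | 240 | no (240 = 240) | yes (240 > 120) | yes |

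Cases A and B are the gap. Case C shows that it closes if enrollment stops before a third subject takes the failed dose alone. Case D is ordinary agreement. Case E is the reverse disagreement. It can arise because Section 8.1.2.1.2 lets 2 evaluable subjects suffice for a decision if neither had related toxicity above Grade 1.

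**Width of the gap** (failed dose minus highest tolerated dose, failed dose included):

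- 240 mg fails after 120 mg: 240 − 120 = 120 mg.
- 480 mg fails after 240 mg: 480 − 240 = 240 mg.
- 720 mg fails after 480 mg: 720 − 480 = 240 mg.

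Cohorts opened after a DLT have 3 to 6 subjects. The documents give no single-agent DLT rate, so the frequency cannot be estimated.

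**Check of the proposed rule.** A dose tolerated in at least 3 subjects has been evaluated in at least 3, so *S* ≤ *E*. It has also been tolerated, so *S* ≤ *T*. The common rule therefore calls for a Lead-in whenever either present rule does.

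**The case against.** The strongest reply is that little turns on this. The outcome-based rule appears in the synopsis and throughout Section 8, and Section 8.1.2.1 refers to Table 3-2 for assessments. Under Section 8.1.2.1.8 the next regimen is agreed by the sponsor and investigators, who would know that a Lead-in had failed. By construction, at least 3 subjects already have single-agent data at an equal or higher dose. Overdose control still limits the dose, and Cycle 1 keeps Day 2 ECGs before and after VX-984. All of this stands and holds the severity down. It does not reconcile two operative rules that give opposite answers.

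It could also be said that 360 mg after 480 mg is a reduction, so nothing is escalated. But the body text compares with the highest tolerated dose, and Figure 8-1 note a says exceeds. 360 mg exceeds 240 mg.

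A reader might infer more than the documents support:

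- *That the schedule forbids a Lead-in in the gap.* It says when there will be one and does not exclude others.
- *That the footnote is always the laxer text.* Case E shows the opposite, so deleting its 3-subject count would remove a safeguard.
- *That the gap covers dose level -1.* Table 8-1 note b says "Dose level -1 represents a dose that may be evaluated if dose level 1 (starting doses of VX-984 and PLD) is poorly tolerated". That level keeps VX-984 at 120 mg and lowers PLD to 30 mg/m². If 120 mg failed alone, there is no tolerated dose to escalate beyond, so the body text is unclear and cannot be said to require a Lead-in.
- *That added subjects in the same cohort are exposed.* The within-cohort waiver already requires that no DLT was seen.

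**Conclusion.** The Protocol is wrong as written on this point, at low severity. Two unreconciled triggers lead to different instructions. The safety-relevant conflict arises only if at least 3 subjects took the failed dose alone, the dose was not tolerated alone, and a new cohort opens above the highest tolerated dose and no higher than the failed one. With Table 8-1 doses the affected range is 120 or 240 mg wide. DLTs seen only with PLD do not create it, because the dose was then tolerated in the Lead-in. The reverse conflict needs a dose tolerated alone by fewer than 3 subjects.

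The conclusion assumes that a dose is either tolerated or not in a Lead-in. The documents leave this undefined. The nearest criterion is the no-DLT condition in the within-cohort waiver, and a single DLT on VX-984 alone need not rule a dose out under the Bayesian model. No sample size, power or model quantity changes.

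**What to change.** Reword Table 3-2 footnote a so that a Lead-in applies to: *all cohorts in Part A in which the VX-984 dose is higher than the highest dose previously tolerated (no DLT on VX-984 alone) in a Lead-in Period in at least 3 subjects.* Use the same rule in the synopsis, Section 8.1 with Figure 8-1 note a, and Sections 8.1.2.1.1 and 8.1.2.1.2. This keeps the outcome condition of the body text and the count of the footnote, as the within-cohort waiver already does. If the sponsor means something looser than no DLT by tolerated, the definition should be stated there instead.

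The cost is a wording amendment in a few places. Compared with the body text, it adds a Lead-in in the rare case where fewer than 3 subjects tolerated the dose alone. It does not increase the number of subjects.
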